**Time Schedule**

Patient inclusion: 01.12.2020

End of study: 01.12.2022

**List of abbreviations:**

CT, computed tomography

DXA, dual-energy X-ray absorptiometry

DNL, de novo lipogenesis

EF, ejection fraction

FF %, fatty fraction

FFA, free fatty acids

GLP-1-receptor agonist, glucagon-like peptid 1 agonist

IHTG, intrahepatic triglyceride

HCC, hepatocellular carcinoma

LPL, lipoprotein lipase

MRS, magnetic resonance spectroscopy

MS, metabolic syndrome

NAFLD, non-alcoholic fatty liver disease

NAFL, non-alcoholic fatty liver

NASH, non-alcoholic steatohepatitis

PET, positron emission tomography

BG, blood glucose

T2DM, type 2 diabetes mellitus

TG, triglyceride

VLDL, very low-density lipoproteins

## Background

### *NAFLD*

Type 2 diabetic patients and obese subjects with upper-body fat distribution have increased risk of heart disease (ischemia and heart failure), insulin resistance (1,2), dyslipidemia (high plasma triglycerides (TG) and low HDL-cholesterol concentrations), abnormal metabolism of free fatty acids (FFA) and very often, increased liver fat content (3). The latter, non-alcoholic fatty liver disease (NAFLD) is considered the hepatic manifestation of the Metabolic Syndrome (MS). NAFLD covers a spectrum from simple reversible hepatic steatosis (i.e. non-alcoholic fatty liver (NAFL) to inflammation and fibrosis, termed non-alcoholic steatohepatitis (NASH). The latter is considered a state of “burned out” NAFLD with gradual loss of hepatocytes with increased risk of progression to cirrhosis and end-state liver disease (4,5, 43-46). NASH and especially NASH with fibrosis, is associated with excess mortality (43-46). Several studies also indicate that NAFLD is associated with development of cardiac steatosis, reduced left ventricular function and cardiac arrhythmia (6-11).

NAFLD is the most common chronic liver disease in the Western world with a prevalence between 17-45 % (47). The estimated prevalence of NAFLD has been shown to mirror the increasing population prevalence of obesity and MS with prevalence rates of NAFL corresponding to 40 %, 30-50 % and 50-90 % in upper-body obese, insulin resistant and dyslipidemic subjects, respectively (with even greater prevalence in type 2 diabetic patients), whereas the prevalence of NASH is reported to be somewhat lower (12). It is not clear whether steatosis leads to NASH or if NASH is developed independently of steatosis – a study however has showed that steatosis progress to NASH in 25 % of patients with NAFL over 3 year (48). The mechanisms behind why some subjects progress from NAFL to NASH are poorly understood, but may involve differences in hepatic fatty acid (FA) trafficking, resulting in an unhealthy balance between FA uptake and increased FA synthesis (*de novo lipogenesis*, DNL) in liver vs. oxidation and export of FA from liver to plasma in “very low-density lipoproteins”-triglyceride (VLDL-TG) particles. The changed hepatic metabolism of fatty acids may in turn promote pro-inflammatory and oxidative stress conditions with degeneration and inflammation of the normal liver architecture (51, 52).

### *NAFLD and risk of cardiovascular disease*

Mediators linking NAFLD with myocardial dysfunction are not known but are presumed to include both pre-hepatic (e.g. ectopic/cardiac fat) and hepatic mechanisms with potential direct

impact on cardiac function and mirrored at the whole body level by metabolic inflexibility. Metabolic inflexibility is the inability to shift efficiently between glucose and lipid oxidation due to a chronic increase in plasma FFA caused by insulin resistant anti-lipolysis and hepatic VLDL-TG hypersecretion (13).

The metabolic dysfunction of the myocardium in NAFLD and T2DM includes 1) reduced basal and insulin stimulated glucose oxidation, 2) reduced phosphate creatinine/adenosine triphosphate (PCr/ATP) ratio (a marker of the myocardial fuel utilization) and 3) a potential reduced FFA oxidation (9,19). Both intrahepatic TG and TG secreted into the bloodstream as lipoproteins (VLDL-TG) are derived from plasma FFA and released into the bloodstream via lipolysis in peripheral adipose tissue (21). Human studies suggest that the circulating FFA in combination with insulin resistance determine the amount of VLDL particles produced by the liver and, hence the quantity of TG released into the blood (22, 27). During basal fasting, the amount of visceral fat correlates directly to the delivery of liver FFA from the circulation (yet with significant difference between men and women) (2).

#### *Insulin resistance and its role in the pathogenesis of NAFLD*

Immediately after a meal, insulin increases and, in healthy people, reduces blood glucose (BG) and results in an almost immediate halt in VLDL secretion. The effect of insulin is, however, severely impaired in NAFL, NASH and type 2 diabetic patients both in the liver (23,28), adipose tissue (24-26), and skeletal muscle (27). The overall effect is an increased amount of VLDL-TG in the blood with subsequent risk of atherosclerosis and ectopic fat accumulation in e.g. the myocardium (10). Although the effect of reduced insulin sensitivity on increased FFA and VLDL-TG levels are well-documented (28), it is uncertain to what extent each factor contributes quantitatively to NAFLD due to the liver's anatomical localization and the lack of robust tracer methods to assess VLDL-TG production rate. Even though NAFLD is recognized as a strong predictor of CVD risk factors associated with MS (5), this is, however, not always the case, and has led researchers to question whether NAFLD is the result of insulin resistance or whether insulin resistance is secondary to NAFLD, or both (29). Studies have shown that the degree of NAFLD in obese, insulin resistant subjects correlates with cellular and intracellular insulin resistant manifestations in many metabolic processes. This is the case in both liver, muscle, and adipose tissue, such as FFA uptake in liver and muscle, hepatic de novo lipogenesis, altered lipogenic enzyme activity in liver and adipose tissue, muscle, mitochondrial/TCA cycle activity, and cardiac steatosis with impaired ventricular function (10, 31, 32). The multiple direct and sometimes temporary relationships between NAFLD and the

heart and peripheral tissues indicate that insulin resistance and metabolic inflexibility is a key component of NAFLD, but also that significant integrated pathophysiological cross-talk exists between the heart, liver, skeletal muscle and adipose tissue. Thus, insulin resistance in combination with hyperinsulinemia and increased hepatic FFA delivery may promote liver fat accumulation by increasing hepatic TG production and de-novo lipogenesis (12, 21, 24, 33). In addition, the development of NAFLD is also assumed to be an imbalance between hepatic FA delivery (FA uptake and/or de-novo synthesis) and hepatic lipid export (i.e hepatic FA oxidation and/or VLDL-TG secretion) as previously described.

In this study we aim at identifying potential differences between patients with T2DM with and without NAFLD, when compared to FA oxidation of the heart, hepatic FA metabolism (uptake, oxidation and re-esterification), and hepatic VLDL-TG kinetic. In addition, muscle and adipose tissue biopsies will be taken out to determine the content of lipid and lipolytic and lipogenic enzymes, as insulin resistant conditions potentially have a substantial effect on the cellular regulation of lipolysis and substrate oxidation of the skeletal and adipose tissue.

We have developed a technique to radioactively label VLDL-TG. The technique involves isolating of the VLDL particles from plasma by ultracentrifugation and incorporation of [ $^{14}\text{C}$ ]-triolein in the particles. The labelled VLDL-TG can hereafter be infused to determine the turnover of VLDL-TG (23,58). We have similarly implemented a method to determine the organ-specific FA uptake and oxidation by PET (positron emission tomography) scan with [ $^{11}\text{C}$ ]-palmitat. The method with PET scan has previously been used to determine FA uptake and oxidation of the heart (20) as well as of the liver (21-23)

The combination of the tracers makes it possible to determine the turnover of FA and VLDL-TG simultaneously.

## **Hypothesis**

We hypothesize that the heart fuel utilisation and FA turnover and hepatic lipid kinetic (FA and VLDL-TG) in relation to NAFL and NASH are abnormal in a coordinated manner in patients with T2DM and is related to myocardial function, intrahepatic triglyceride (IHTG) content and adipose and skeletal lipid metabolism.

## **Specific aims**

To determine differences in subjects with T2DM with and without NAFLD in relation to:

- FA uptake and oxidation in the heart
- Hepatic FA uptake and oxidation
- Secretion and oxidation of VLDL-TG
- Identification of potential coordinated changes in the metabolism in heart, liver, skeletal and adipose tissue.

## **Materials and Method**

### **Inclusion criteria**

- 20 study participants with T2DM (definition (49)) will be recruited:
- Group 1: 10 men/women with NAFL and/or NASH, confirmed fat fraction (FF) % > 5,6 assessed using MR spectroscopy (MRS)
- Group 2: 10 men/women matched for age and BMI without NAFLD (definition (47))
- Age of 30-70 years
- Non-smokers
- Written consent before the study start

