### **Exclusion criteria**

- Comorbidity other than hypertension and dyslipidaemia
- Fixed medical drug consumption (including insulin) except statins and anti-diabetic medications. However, statins and weekly based GLP-1 agonist must be paused 1 week before the examination date and other antidiabetic medication 3 days before the study date.
- Patients with cancer or former cancer patients
- Blood donation within the last 3 months prior to the study
- Participation in experiments involving radioactive isotopes within the last 3 months
- Alcohol abuse (over 21 items per week for men and over 14 for women) or other substance abuse
- Pregnancy

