**- Magnetic resonance spectroscopy (MRS)**

MRS is used to quantify the hepatic and cardiac fat content and ATP/AMP ratio. A fat content of more than 50 mg/g corresponding 5 % of the wet weight is diagnostic for hepatic steatosis,

measured by MRS as FF % > 5,6 (23). MRS is used to distribute the participants into group 1 and group 2.

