## **Primary Endpoint**

- FFA uptake and oxidation as well as energy utilization in the heart ([11C] palmitate PET)

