### **Statistical analysis**

Sample sizes are based on estimates of cardiac palmitate from two recent studies in type 2 and nondiabetic men (28,29), as well as on prior experience regarding mean basal VLDL-TG secretion of 60  $\mu\text{mol}/\text{min}$  (SD of diff: 10  $\mu\text{mol}/\text{min}$ ). To detect a difference in palmitate oxidation as well as on VLDL-TG secretion between 2 experimental days of 20% (12.5 (SD 6.25)  $\mu\text{mol}/\text{min}$ ) with power 0.80 and  $\alpha$  5%, seven subjects are needed using two-sample t-test. Group comparisons will be done with standard statistical methods (ANOVA, t-test for parametrical data) and p-value under 0,05 will be assumed to be statistical significant. Corrections will be examined using Pearson's or Spearman's test. With 10 participants in each group, we would be able to determine a 30 % increased uptake of FFA in liver in subjects with NAFLD (power: 0.80). This is based on estimates of palmitate uptake in liver and FA oxidation in the heart from our previous studies, where we used the same  $^{11}\text{C}$ -palmitate tracer (37,50).

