### **The scope of the screening activity**

We expects to screen 30 potential candidate participants, who full fill inclusion criteria with scans and blood samples to obtain 20 participants. The test results from the blood samples from screening of volunteers who are being included or excluded, will be available in the volunteers electronic patient journal (MidtEPJ). If the blood samples or scans gives rise to further investigation, the participant will be contacted by phone and informed to contact a medical doctor/or be referred to the relevant medical speciality.

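### Sex is neither a matching factor nor a prespecified model term in the non-randomised 10 v 10 comparison; a sex term and a qualified balance clause are a cheap improvement

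*Combined protocol and SAP*

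**What the plan says.** - **Group formation.** The section on magnetic resonance spectroscopy states: "MRS is used to distribute the participants into group 1 and group 2". Nothing is allocated at random.
- **Matching.** The Inclusion criteria describe the control group as "Group 2: 10 men/women matched for age and BMI without NAFLD". Group 1 is also open to both sexes. The wording says who may enter; it sets no sex quota, ratio or matching rule.
- **Analysis.** The Statistical analysis section says "Group comparisons will be done with standard statistical methods (ANOVA, t-test for parametrical data"). No sex factor, covariate or stratification is named there or elsewhere.
- **Primary endpoint.** It is cardiac: "FFA uptake and oxidation as well as energy utilization in the heart".
- **Sex in the background.** The section on NAFLD and cardiovascular risk says that visceral fat correlates with hepatic FFA delivery in the fasting state, "yet with significant difference between men and women". It gives no size and says nothing about the heart in this respect.
- **Screening pool.** "We expects to screen 30 potential candidate participants", from whom 20 are to be obtained.

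**The concern.** In a randomised trial, chance imbalance in sex is covered by the error rate of the test. Here only matching and modelling protect the comparison, and neither mentions sex. Two things follow if sex affects the outcome. If the sex mix differs between groups, the unadjusted difference combines a sex difference with the NAFLD difference, and may create or hide an effect. If the mix is the same but sex is left out of the model, the variation due to sex stays in the error term and power falls. With 10 per group, one or two participants change the balance. An imbalance noticed afterwards leaves a choice between an unadjusted result open to confounding and an adjustment chosen after seeing the data.

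**Working it through.** **Inputs from the documents.** 10 per group; α 5% (taken as two-sided, since sidedness is not stated); power 0.80; difference 12.5 with SD 6.25 μmol/min; a 30% increase in liver FFA uptake detectable with 10 per group.

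**Inputs assumed.** An additive sex effect g of 0 to 1.2 within-sex SD; the number of men in each group binomial, with 50% to 70% men. The documents give neither.

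**1. The plan's own figures.** The stated difference gives d = 12.5/6.25 = 2. A two-sided two-sample t-test then needs 6 per group for power of at least 0.80; 7 per group gives 0.929 and 10 per group gives 0.988. The stated seven is close if read as per group. The 30% statement gives no SD, so it cannot be reproduced. Power of 0.80 with 10 per group implies d = 1.325, that is a coefficient of variation of 0.30/1.325 = 0.226. Both values of d are used below, because the section supports both and its inputs do not settle which applies.

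**2. Bias of the unadjusted difference.** Bias = (gap in men/10) × g.
- 7 v 3: 0.4 × 0 to 0.4 × 1.2 = 0 to 0.48 SD.
- 6 v 4: 0.2 × 0 to 0.2 × 1.2 = 0 to 0.24 SD.

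**3. Type I error of the unadjusted t-test (simulated, fixed split).**

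| Split (men) | g = 0 | g = 0.5 | g = 0.8 | g = 1.0 | g = 1.2 |
|---|---|---|---|---|---|
| 6 v 4 | 0.050 | 0.048 | 0.045 | 0.044 | 0.040 |
| 7 v 3 | 0.050 | 0.064 | 0.081 | 0.096 | 0.109 |

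At 6 v 4 the unmodelled sex variation widens the standard error enough to offset the bias. The model with group and sex stays at about 0.050 throughout, as it must when the simulated effect is additive.

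**4. How likely is a large gap?** With the same mix in both groups, the probability of a gap of 4 or more men is 0.115, 0.108 and 0.085 at 50%, 60% and 70% men. A gap of at most 2 has probability 0.74 to 0.78. Averaged over all splits, the unadjusted test then keeps 5.0%. If the mixes differ, say 70% v 50% men, a gap of 4 or more has probability 0.25 and the average error is 5.5% to 7.4% for g of 0.5 to 1.2.

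**5. Power for g from 0.5 to 1.2.** The adverse case is 3 v 7 men, with the sex effect opposing the NAFLD effect.

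| d | Split | Unadjusted | Group + sex |
|---|---|---|---|
| 1.325 | 5 v 5 | 0.78 to 0.68 | 0.80 |
| 1.325 | 3 v 7, adverse | 0.64 to 0.32 | 0.73 |
| 2 | 5 v 5 | 0.985 to 0.970 | 0.988 |
| 2 | 3 v 7, adverse | 0.96 to 0.82 | 0.97 |

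**6. Price of the sex term if sex explains nothing (d = 1.325).** Error degrees of freedom go from 18 to 17. The variance of the group difference is multiplied by 1/(1 − r²), where r is the correlation of group with sex, equal here to gap/10 for splits symmetric about 5.
- 5 v 5: factor 1.00, power 0.800 to 0.797.
- 6 v 4: 1/(1 − 0.04) = 1.04, power 0.781.
- 7 v 3: 1/(1 − 0.16) = 1.19, power 0.726.

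**The case against.** **No evidence that sex matters for the primary endpoint.** This stands. A reader might infer from the background that sex is a known confounder of cardiac fatty acid uptake. The documents do not support that: the remark concerns hepatic FFA delivery, is unquantified, and describes a difference in a relationship. A main-effect sex term removes a difference in means, not a difference in slope. If g is 0 there is no harm.

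**The planning data come from men.** The section says "Sample sizes are based on estimates of cardiac palmitate from two recent studies in type 2 and nondiabetic men", and a reader might infer that the whole sample size ignores variation between the sexes. It does not follow. The same section supports 10 per group with a second basis, earlier work on liver palmitate uptake and cardiac fatty acid oxidation (references 37 and 50), for which no sex restriction is stated. The remark reaches only the first set of estimates (references 28 and 29) and is not relied on here.

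**The worst case is a tail.** This stands too. With the same mix, a gap of 4 or more in the adverse direction has probability 0.042 to 0.058, and power of 0.32 also needs g = 1.2 at the smaller d. At d = 2 the losses are much smaller.

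**Adjustment is not always better.** At 3 v 7 with g of 0 to 0.2, the unadjusted test has power of 0.80 to 0.75 against 0.73 for the adjusted model, even in the adverse direction.

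**ANOVA allows a sex factor, and controls could be balanced informally.** True. The gap is one of prespecification, which matters because the choice would otherwise be open after the split is known.

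**Conclusion.** The omission is real: the groups are not randomised, sex is not matched, and no sex term is named. It is a cheap improvement rather than a flaw shown to invalidate the plan. Its size is conditional. For an assumed sex effect of 0 to 1.2 SD, a 7 v 3 split gives a bias of 0 to 0.48 SD and a type I error of 5% to 11%. At 6 v 4 the bias is at most 0.24 SD, without inflation.

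A reader might infer that the test as planned has an inflated error rate overall. The figures do not support this when both groups are drawn with the same sex mix, where the average is 5.0%. Inflation on average needs both a sex effect and different mixes, and the documents give neither. The gain in power from adjusting depends on which effect size is meant: it is material at d = 1.325 and at most modest at d = 2 except in the adverse split with a large sex effect.

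**What to change.** **Statistical analysis.** Add: *Groups will be compared with a linear model with group and sex, reporting the sex-adjusted difference with its 95% CI, and the unadjusted difference alongside.*

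**Inclusion criteria, Group 2.** After the age and BMI matching, add: *and, where the screened pool allows, balanced for sex.* Where balance cannot be reached, the sex term is the fallback.

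**Cost.** No new data are needed; sex must already be known to apply the alcohol exclusion ("Alcohol abuse (over 21 items per week for men and over 14 for women"). The model spends one error degree of freedom, with the power loss shown in step 6. At 7 v 3 with no sex effect, the unadjusted test would have had more power.

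Selection becomes somewhat harder. At an assumed NAFLD share of 50% to 65%, 30 screened yield at least 10 per group with probability 0.96 falling to 0.64 under the present plan. Requiring the numbers of men to differ by at most one lowers this by 0.01 to 0.02 if the sex mix is the same, and by 0.09 to 0.10 at 70% v 50% men. These figures ignore age and BMI matching, so the feasibility probabilities are upper bounds. That is why the balance clause is qualified rather than absolute.

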### **Exclusion criteria**

- Comorbidity other than hypertension and dyslipidaemia
- Fixed medical drug consumption (including insulin) except statins and anti-diabetic medications. However, statins and weekly based GLP-1 agonist must be paused 1 week before the examination date and other antidiabetic medication 3 days before the study date.
- Patients with cancer or former cancer patients
- Blood donation within the last 3 months prior to the study
- Participation in experiments involving radioactive isotopes within the last 3 months
- Alcohol abuse (over 21 items per week for men and over 14 for women) or other substance abuse
- Pregnancy

## **Study participants will be omitted from the study if**

- They choose to
- There are serious or intolerable side effects during the study
- Study participants develop conditions mentioned under "exclusion criteria".

## **Recruitment**

[figure not shown]
Recruitment will be done via notice at Aarhus Universitetshospital ([www.auh.dk](http://www.auh.dk)), Aarhus Universitet ([www.au.dk](http://www.au.dk)) and other educational institutions in Aarhus as Aarhus Business College ([www.aabc.dk](http://www.aabc.dk)), Aarhus teknisk Skole ([www.aarhustech.dk](http://www.aarhustech.dk)), VIA University College Aarhus ([www.via.dk](http://www.via.dk)), by announcing in patient association ([www.diabetes.dk](http://www.diabetes.dk)) and in newspapers such as Jyllands-Posten, Aarhus Stiftstidende and Lokalavisen, via social media (Facebook) and via homepage [www.forsøgsperson.dk](http://www.forsøgsperson.dk).

Recruitment and information about the study will also be done via medical doctors from outpatient clinics at The Department of Endocrinology and Internal Medicine and The Department of Hepatology and Gastroenterology, AUH.

The candidate participants will be informed about the project either by telephone or orally in the outpatient clinics. In addition, they will receive the "Project Information" and "Information material from The Denmark Central Region Committees on Health Research Ethics". Candidate participants will be contacted after prior agreement by telephone and will be invited to an information meeting. The participant can bring an assessor to the meeting.

All information about the study will be given by investigator [name] and if the participant accepts final participation, a declaration of consent is signed.

## Flow chart

## Screening

The purpose of the visit is to evaluate inclusion and exclusion criteria. Prior to the visit, the potential candidate participant has already received written information material about the project. The potential candidate will be informed orally. If the participant accepts final participation and is eligible to participate in the study, a declaration of consent is signed. Furthermore, during this visit following will be obtained:

**- Medical history and examination (incl. Weight, height, blood pressure and pulse), blood tests (plasma glucose, hemoglobinA1C, lipid profile, SD163, haematological parameters, TSH, ALAT, ASAT, alkaline phosphatase, eGFR, creatinine, sodium and potassium).**

